8.2.1 Analysis populations

- Intention-to-treat population: All randomized patients will be analyzed in the arm they were allocated by randomization.
- Per protocol population: All patients who are eligible and have started their allocated treatment (at least one dose of the study drug(s) in chemotherapy trials)
- Safety population: All patients who have started their allocated treatment (at least one dose of the study drug(s) in chemotherapy trials)

A patient will be considered to be eligible if he/she did not have any deviation from the patient entry criteria listed in chapter 3 of the protocol. Potential eligibility problems will be assessed by the Clinical Research Physician at time of medical review.

8.2.2 Statistical methods

Analysis of the primary endpoint

The primary analysis will be performed to per-protocol population.

Patients with success is defined by the primary endpoint in Section 7.2.1. The PFSR-OSI-18 in each arm and their 84% confidence intervals will be provided. In case the number of patients analyzed in each arm exceeds or less than what is foreseen above (Section 8.1.1), the 84% confidence interval will be used for the decision.

Time to event endpoints

The analyses of the primary and secondary endpoints will be performed on per-protocol population. Comparison between arms are foreseen for BPFS endpoint only.

Estimates and confidence intervals

Estimates of the median PFS-OSI, TTP-OSI, PFS2-OSI and OS are obtained by the Kaplan Meier technique. The 84% and 95% confidence intervals (CI) for the median will be calculated using the reflected CI method.

Estimates of the event-free rate at fixed time point (18 months) will be obtained using the Kaplan Meier technique and 84% 2-sided CI will be calculated by Greenwood's estimation of the standard deviation. Estimates of hazard ratios and their 84% 2-sided CI will be obtained by Cox regression. In addition 95% 2-sided CI will be provided for both the estimates of event rates and hazard ratios. Kaplan Meier Curves will be drawn for both the experimental and control arms on the same plot.

Inference: Test statistics for comparisons (for BPFS)

Cox regression (Score Test) will be used to compare the experimental versus the control arms adjusted by the stratification factors in randomization (except for centers) at 1-sided 10% significant level.

Toxicity

Analysis for toxicity is based on the safety population. The worst grade of toxicity/adverse events observed over the whole treatment period (excluding re-challenge period for Arm A) according to CTCAE version 4 will be displayed. No formal statistical analysis will be performed to compare toxicity in both arms.

Response Rate

Patients with response categories progression, early death and unknown will be considered as failing to respond to treatment. The response rates in each arm and their 95% confidence intervals will be provided. In addition, response rates in the 2 arms will be compared using a two-sample test at 5% 2-sided level.

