- Any of the following cardiac criteria:
 - Mean resting corrected QT interval (QTc) >470 msec, obtained from 3 ECGs using local clinic ECG machine-derived QTcF value
 - Any clinically important abnormalities in rhythm, conduction, or morphology of resting ECG, e.g., complete left bundle branch block, third-degree heart block, second-degree heart block, PR interval >250 msec or history of episodes of bradycardia (<50 BPM);
 - Any factors that increase the risk of QTc prolongation or risk of arrhythmic events such as heart failure, hypokalaemia, congenital long QT síndrome family history of long QT syndrome, or unexplained sudden death under 40 years of age in first-degree relatives or any concomitant medication known to prolong the QT interval.
 - Abnormal cardiac function: LVEF <50% (assessed by MUGA or ECHO)
- Past medical history of ILD (Interstitial Lung Disease), drug-induced ILD, radiation pneumonitis which required steroid treatment, or any evidence of clinically active ILD.

4 Trial Design

This is an open-label, randomized, three-armed, multicentric, phase II study in *EGFR* mutant advanced NSCLC patients.

[figure not shown]
Patients will first be registered into the EORTC ORTA system (registration = step 1) after signing the informed consent form and completion of all screening tests and confirmation of eligibility criteria for registration. The site will immediately send the blood samples for circulating free DNA EGFR T790M (cfDNA T790M) testing to the central lab (within 24 hours at maximum) at the Medical University of Gdansk (Poland). Once the sample is assessed and acknowledged for adequacy by the central lab, the result is entered in ORTA by EORTC (step 2), the site will be notified whether they can further proceed to patient randomization in the EORTC ORTA system. Should the sample not be deemed adequate by the central lab the site will be requested to send another blood sample for testing. Patients will be randomized (step 3) after verification of all eligibility criteria to receive one of the following:

- Osimertinib (arm A) until PD according to RECIST 1.1;
- Gefitinib until emergence of positive T790M status ("cfDNA T790M positive progression") (arm B) followed by osimertinib until second PD according to RECIST 1.1;
- Gefitinib until PD according to RECIST 1.1 followed by osimertinib until PD according to RECIST 1.1 (arm C).

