8.1.2 Power to detect a difference in brain progression free survival (BPFS)

In this study, a special emphasis is given to the secondary endpoint BPFS. Formal comparison between arm A versus B and A versus C with respect to BPFS will be made. The power of such comparison is given below.

With a 1-sided alpha = 5% (so that a 1-sided family wise error: 10%, taking into account 2 comparisons), and looking for an improvement in BPFS at 18 months from 75% to 87.5% (equivalent to 54% reduction in risk of progression, i.e. HR = 0.46), 36 BPFS events will give an approximately 70% power to detect the above difference.

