8.2.3 Pre-planned sensitivity or exploratory analyses

A sensitivity analysis of efficacy based on intent to treat (ITT) population will be conducted in addition to the primary analysis based on per protocol population.

Sensitivity analyses will be conducted on PFS-OSI rate at 18 months according to RECIST 1.1 (primary endpoint) to verify the robustness of the results vis-à-vis the missing data. Once the main analysis is completed, PFSR-OSI-18 will be analyzed as binary endpoint. The following sensitivity analyses will be conducted:

- Patients lost-to-follow up before 18 months, i.e. with missing assessments at 18 months (using the window of ± 2 weeks) and at all times thereafter will be considered as having an event at 18 months (worst case scenario). Only patients with the confirmation they are alive and progression free at 18 months (status for PFS not missing at 18 months or after and status at 18 months is no progression) will be considered event free at 18 months.
 In details,
 - Patients alive and without any progression by RECIST 1.1 at 18 months will be counted as a success irrespective of treatment(s) received (still under protocol treatment or switched to investigator's choice standard treatment including no further systemic anticancer therapy documented).
 - Patients who progress on gefitinib by RECIST 1.1 or by positive cfDNA T790M status testing prior
 to 18 months and are switched to osimertinib (T790M positive) and progression free at 18 months
 after switching to osimertinib will be counted as a success.
 - Patients who progress on gefitinib by RECIST 1.1 or by positive cfDNA T790M status prior to 18 months and are switched to osimertinib (T790M positive) and progress by RECIST 1.1 after switching to osimertinib prior to 18 months will be counted as a failure.
 - Patients with a progression by RECIST 1.1 prior to 18 months and not able to start osimertinib prior to 18 months for any reason will be counted as a failure.
- Complete case analysis: the analysis will be restricted to patients with available PFS data at 18 months (complete case analysis).

In addition, sensitivity analyses will be conducted in which patients who will have started any other cancer treatment before their disease progresses will be considered as having an event at the date of start of the other cancer treatment.

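### The powered BPFS comparison is analysed primarily on a per-protocol set settled after open-label allocation; all randomised patients should be the primary set

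*Combined protocol and SAP*

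**What the plan says.** Section 8.2.2 sets one population for all efficacy endpoints: "The analyses of the primary and secondary endpoints will be performed on per-protocol population". It continues: "Comparison between arms are foreseen for BPFS endpoint only". Section 2.4.2 lists BPFS as a secondary endpoint, so the rule applies to it.

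Section 8.1.2 gives BPFS a special place: "Formal comparison between arm A versus B and A versus C with respect to BPFS will be made". It plans 36 events for about 70% power at one-sided 5% per comparison, to detect a rise in 18-month BPFS from 75% to 87.5% (HR 0.46).

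Section 8.2.1 defines the analysis set: "Per protocol population: All patients who are eligible and have started their allocated treatment". One dose is enough. On eligibility it adds: "Potential eligibility problems will be assessed by the Clinical Research Physician at time of medical review". It does not say whether that assessment is made without knowledge of arm or outcome. Chapter 4 begins: "This is an open-label, randomized, three-armed, multicentric, phase II study".

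ITT appears in section 8.2.3: "A sensitivity analysis of efficacy based on intent to treat (ITT) population will be conducted in addition to the primary analysis".

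Under response rate, section 8.2.2 also says that "response rates in the 2 arms will be compared using a two-sample test at 5% 2-sided level". This conflicts with the limitation to BPFS and needs to be reconciled.

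**The concern.** Per-protocol fits the single-arm rule of 25 successes in 49, because section 8.1.1 sizes that rule on eligible patients who started treatment. The plan carries the same set over to a randomised comparison and gives no reason. BPFS is timed from randomisation (section 7.2.9), yet membership of the set depends on two things settled later.

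- **Starting the allocated drug.** Patient and site know the arm by then, and the first drug differs: osimertinib in arm A, gefitinib in arms B and C (section 5.3).
- **Eligibility as ruled at medical review.** Section 9.2.1 has this review run regularly during the study. Section 8.2.1 makes any deviation from the entry criteria disqualifying, while section 3.1.2 accepts margins of 5% for haematology, 10% for biochemistry and 3 days. That leaves room for judgement.

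If either step removes different kinds of patient from different arms, the hazard ratio is biased. If the per-protocol and ITT results then disagree, the plan makes per-protocol the leading one.

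**Working it through.** **Inputs.** From section 8.1.1: 52 randomised and 49 per-protocol patients per arm, 26 months of accrual, 24 months of further follow-up. From section 8.1.2: BPFS 75% vs 87.5% at 18 months, 36 events, one-sided 5%. Assumed here: exponential BPFS, uniform accrual, no loss to follow-up. Section 8.2.2 gives a one-sided 10% level for the BPFS test; I use 5%, the level behind the stated power.

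**1. The plan's own figure.** HR = ln(0.875)/ln(0.75) = 0.464. Freedman power = Φ(√d × (1 − HR)/(1 + HR) − 1.645).
- d = 36, HR 0.46: Φ(6 × 0.54/1.46 − 1.645) = Φ(0.574) = 71.7%.
- d = 36, HR 0.464: Φ(6 × 0.366 − 1.645) = Φ(0.551) = 70.9%.

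The stated figure of about 70% is reproduced.

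**2. Expected events in each population.** With λ = −ln(S18)/18, the event probability is p = 1 − (e^(−24λ) − e^(−50λ))/(26λ).
- S18 = 0.75: λ = 0.01598, p = 0.442.
- S18 = 0.875: λ = 0.00742, p = 0.239.
- The sum is 0.681 per pair of patients: 49 × 0.681 = 33.4 events per-protocol and 52 × 0.681 = 35.4 ITT.

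The planned 36 events lie closer to the randomised number.

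**3. Power (HR 0.464).**

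| Follow-up after last entry | Per-protocol (2 × 49) | ITT (2 × 52) |
|---|---|---|
| 24 months | 33.4 events, 68.1% | 35.4 events, 70.3% |
| 18 months (the stated minimum) | 28.9 events, 62.7% | 30.7 events, 64.9% |

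The gap is about 2 points either way, if the added patients are followed and show the same effect.

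**4. If the added patients do not show the same effect.** Take 36 per-protocol events and HR 0.46 (71.7%) as reference. ITT would have 36 × 104/98 = 38.2 events.
- Same effect: 73.9%.
- The 3 added arm A patients have control-arm BPFS: S18 = (49 × 0.875 + 3 × 0.75)/52 = 0.868, HR = ln(0.868)/ln(0.75) = 0.493, power 67.5%.
- The same dilution, with no events at all from the added patients (36 events): 65.3%. This is deliberately pessimistic, since patients without events can hardly dilute the effect.

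ITT therefore changes power by between about +2 and −6 points.

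**5. Informative exclusion.** Suppose no true effect and 13 of 52 events per arm by 18 months (S = 0.75). Remove k patients with events from one arm only, so that S = 1 − (13 − k)/(52 − k) there.

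| k | S in that arm | Apparent HR = ln(S)/ln(0.75) |
|---|---|---|
| 1 | 0.765 | 0.93 |
| 2 | 0.780 | 0.86 |
| 3 | 0.796 | 0.79 |

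Three is the planned number of exclusions per arm. By contrast, 3 exclusions per arm unrelated to outcome would remove on average 3 × 0.442 = 1.3 control events and 3 × 0.239 = 0.7 arm A events, which leaves the hazard ratio essentially unchanged.

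**The case against.** The set is mild as per-protocol sets go. One dose qualifies, and patients who later switch, stop or fail to comply stay in their allocated arm. Eligibility rests on entry criteria that are checked one by one before allocation, with actual values requested (section 12.3). Planned exclusions are about 5%. The ITT result will be reported in any case, so a distortion would be visible. BPFS is a secondary endpoint of a phase II trial, and the power difference is about 2 points against a target given only as approximate.

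Most of this stands, and it limits the size of the point. A reader might infer that the plan abandons randomisation, or that the BPFS result will be biased. The documents support neither: they give no rate of refusal or late exclusion by arm, and they are silent on blinding of the review, which is a risk and not evidence of bias.

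A reader might also infer that ITT is free. Chapter 6 sets no clear scan schedule for patients who never start treatment; follow-up imaging is described after the end or interruption of treatment. Section 7.1.4 requires response assessment even of ineligible patients, but fixes no imaging calendar. Such patients may be censored early or may dilute the effect.

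What the objection does not supply is a reason for per-protocol to lead in the randomised comparison. Lower power through honest dilution is not such a reason.

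**Conclusion.** The point holds as a matter of which analysis leads. The trial's only powered comparison between arms rests primarily on a set that depends on decisions made after open-label allocation, without a stated reason. It is not the only between-arm test in the text, since section 8.2.2 also mentions a response-rate test. That test is not powered, and section 7.2.6 leaves patients not given osimertinib out of the response analysis.

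The cost in power at the planned exclusion rate is small: about 2 events and 2 points, under exponential BPFS, uniform accrual and full follow-up. The exposure is to informative exclusion. With about 35 events, one to three selectively removed patients could move a null hazard ratio to between 0.93 and 0.79. That range is a worst-case illustration that requires exclusion of patients with events from one arm only. The planned ITT sensitivity analysis softens the problem but does not settle which result decides. The change is worth making, but the defect does not invalidate the trial.

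**What to change.** In section 8.2.2, and in the matching text of the protocol summary, make ITT (all randomised patients, as allocated) the primary population for the BPFS comparisons between arms. In section 8.2.3, name per-protocol as the sensitivity analysis for BPFS. Keep per-protocol for the single-arm PFSR-OSI-18 decision.

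Two short additions would help: that eligibility for the per-protocol set is ruled on without knowledge of arm or outcome, and how BPFS is censored for patients who never start treatment.

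The cost is wording. It needs no new patients and no new analysis, because both are already planned and only their order changes. The downside is that ITT power may fall a few points below the per-protocol figure if never-starters dilute the effect or have few brain scans, instead of rising by about 2 points. The change should be made before BPFS results by arm are known.

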8.1 Statistical design

8.1.1 Sample size

This study is designed with an understanding of the difficulty of having a primary endpoint which solidly covers all arms. The primary endpoint PFSR-OSI-18 as defined in Chapter 0, will be assessed in all arms, yet this endpoint will be used to evaluate arm B and arm C. With this restriction, the below criteria for a success of the arm (applicable B and C) should be viewed as exploratory and further information from secondary endpoints as well as the costs should be considered if the arm is judged as feasible to be further explored.

The study design is a 1-Stage Ahern Design - Single Proportion, with Progression Free Survival rate at 18 months (PFSR-OSI-18) as primary endpoint. It was designed with a 1-sided alpha = 0.08 and 92% power (beta = 8%).

In arm B and C of this trial, if the result is compatible with a progression free survival rate at 18 months (PFSR-OSI-18) of 60% in the studied population, the strategy should be further explored. However, if we are unable to demonstrate that the PFSR-OSI-18 in the studied population is at least 40%, the strategy should be rejected from further exploration.

49 eligible patients who started treatment are needed in each arm. To declare the arm worthwhile for further exploration, at least 25 out of 49 patients should be a success (see definition of the primary endpoint in section 7.2.1) at 18 months.

Additional 5% patients will be accrued to take into account patients who might be ineligible or not starting treatment. Hence, using a 1:1:1 ratio for randomization, a total of 156 patients will be accrued in this study (52 pts in each arm) within 26 months and an additional 24 months of follow up after the last patient entry is needed to allow the assessment of the primary endpoint. The estimated duration of the study is 6 years, given that all patients have ended their treatment according to End of Study definition (section 8.4).

In this study a minimum of 18 months of follow up is needed after the last patient entry.

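### For any arm size other than 49, the go/no-go rests on an 84% CI whose scale and deciding limit are not stated; on the plain reading, without censoring, the one-sided error exceeds 8% at some sizes (9.8% at n = 50)

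*Combined protocol and SAP*

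**What the plan says.** Section 8.1.1 sets the primary decision for arms B and C: "The study design is a 1-Stage Ahern Design - Single Proportion", with one-sided alpha 0.08, power 92%, an uninteresting rate of 40% and a target of 60%. It states that "49 eligible patients who started treatment are needed in each arm" and that "at least 25 out of 49 patients should be a success". Accrual is 52 per arm, a 5% allowance for patients who are ineligible or do not start treatment. The same section asks that the criteria be viewed as exploratory and weighed with secondary endpoints and costs.

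Section 8.2.2, under the analysis of the primary endpoint, adds that if the number analysed is above or below plan, "the 84% confidence interval will be used for the decision". That sentence names no interval method and no limit. Further on, under time-to-event endpoints, the event-free rate at 18 months is to be estimated by Kaplan-Meier, and an "84% 2-sided CI will be calculated by Greenwood's estimation of the standard deviation". No transformation is named.

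The documents treat missing 18-month assessments in two ways. Section 7.2.1 uses Kaplan-Meier to allow for failures of follow-up. The Protocol summary (Criteria for evaluation, Efficacy) counts patients without an adequate 18-month assessment as failures.

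**The concern.** The 25/49 rule is an exact binomial rule, and its 8% ceiling belongs to n = 49. With 52 randomised per arm, a per-protocol number other than 49 is more likely than not, so the fallback may well be the rule actually used.

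A two-sided 84% interval leaves 8% in each tail, so it looks as if it carries the design alpha over to other sizes. It does so only approximately. At sample sizes near 50, the number of successes needed can differ by one between interval types, and one success moves the error by about 4 percentage points at n = 50. Because the plan does not fix the interval, the same data could pass or fail depending on a choice made at analysis, and on one natural choice the stated error is exceeded.

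**Working it through.** **Inputs.** p0 = 0.40, p1 = 0.60, alpha = 0.08, n = 49, r = 25, 52 accrued per arm (section 8.1.1); 84% two-sided interval, hence z = 1.405 (section 8.2.2). Assumption: an arm passes if the lower limit exceeds 0.40. This is inferred from the 40% criterion in section 8.1.1.

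**Step 1: the plan's own figure.** With X binomial (49, p), P(X ≥ 25 | 0.40) = 7.76% and P(X ≥ 25 | 0.60) = 92.24%. The stated design is reproduced.

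**Step 2: the fallback on its plain reading.** With no censoring before 18 months, Greenwood's standard deviation equals √(p̂(1 − p̂)/n), so the linear lower limit is p̂ − 1.405·√(p̂(1 − p̂)/n). At 25/50 this is 0.50 − 1.405 × 0.0707 = 0.4006, a pass. At 26/52 it is 0.4026, also a pass. For each n, take the smallest r whose lower limit exceeds 0.40. The error is P(X ≥ r | n, 0.40) and the power is P(X ≥ r | n, 0.60). The exact columns do the same with the Clopper-Pearson limit.

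| n | linear: r | error % | power % | exact: r | error % | power % |
|---|---|---|---|---|---|---|
| 44 | 23 | 6.7 | 88.4 | 23 | 6.7 | 88.4 |
| 45 | 23 | **8.6** | 91.4 | 24 | 4.8 | 85.6 |
| 46 | 24 | 6.4 | 89.1 | 24 | 6.4 | 89.1 |
| 47 | 24 | **8.2** | 91.8 | 25 | 4.6 | 86.4 |
| 48 | 25 | 6.0 | 89.7 | 25 | 6.0 | 89.7 |
| 49 | 25 | 7.8 | 92.2 | 25 | 7.8 | 92.2 |
| 50 | 25 | **9.8** | 94.3 | 26 | 5.7 | 90.2 |
| 51 | 26 | 7.4 | 92.6 | 26 | 7.4 | 92.6 |
| 52 | 26 | **9.3** | 94.6 | 27 | 5.4 | 90.7 |

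**Step 3: the scale changes the decision.** At 25/50 the lower limit is 0.4006 on the linear scale, 0.3972 on the log-log scale and 0.3924 by Clopper-Pearson. The first passes; the other two fail. Log-log is not a general remedy: it still accepts 23/45 (8.6%) and 24/47 (8.2%).

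**Step 4: the limit matters too.** Section 8.1.1 also speaks of a result compatible with 60%. The linear interval at 25/50 is 0.50 ± 0.0994, that is 0.4006 to 0.5994. It excludes 40% and also excludes 60%, so it passes on one criterion and fails on the other.

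**Step 5: how likely these sizes are.** Assume each of 52 patients independently has a 5% chance of being non-evaluable. Then n = 50 is the most likely size (about 25.5%), n = 49 has about 22.4%, and the four sizes above 8% (45, 47, 50, 52) together have about 41%.

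**Step 6: censoring.** Simulating exponential event and censoring times under p0 = 0.40 with the linear limit, 5-10% censored by 18 months gives an error of about 7.9-8.1% at n = 50 and 7.8-7.9% at n = 52.

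**The case against.** The case against is substantial, and most of it limits the point without removing it.

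- A reader might infer that the plan prescribes an untransformed interval. It does not. Greenwood's formula is a variance estimator and can feed linear, log or log-log limits. The Greenwood sentence also stands under time-to-event endpoints, apart from the decision sentence. What stands is that the scale is open and that linear is the plainest reading.
- A reader might infer that the error rises to 9.8% whenever n is not 49. It does not. At 44, 46, 48 and 51 the linear and exact rules have the same cut-off and stay below 8%. Averaged over the sizes in step 5, the linear rule's error is about 8.0%. The decision is nevertheless taken at the one size observed.
- The excess needs almost no censoring; about 5% of patients censored removes it. On the other side, section 8.1.1 requires at least 18 months of follow-up after the last patient entry, so administrative censoring should be slight, and the Protocol summary's missing-as-failure rule would remove censoring altogether. Which applies depends on the unreconciled texts in section 7.2.1 and the summary.
- The criteria are exploratory, no arms are compared on this endpoint, and the largest excess is 1.8 points (9.8 − 8.0). This limits the consequence. It is still the only formal decision rule for the primary endpoint.

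**Conclusion.** The point holds as a gap in specification with a modest, size-dependent effect. For n other than 49, section 8.2.2 fixes neither the interval scale nor the limit that decides, so the stated one-sided 8% is not guaranteed. The excess in the working table rests on three assumptions: a linear Greenwood interval, a pass when the lower limit exceeds 40%, and no censoring before 18 months. The documents do not support a claim that the error is generally inflated, or that the 25/49 rule itself is wrong; that rule reproduces exactly. The change is worth making because it is cheap and the most likely arm size, under the plan's own 5% allowance, is the one with the largest excess.

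**What to change.** State in section 8.2.2 that, for n other than 49, an arm passes if the exact (Clopper-Pearson) 84% lower limit for the proportion of successes exceeds 40%. Equivalently, list the cut-offs: 23/44, 24/45, 24/46, 25/47, 25/48, 26/50, 26/51, 27/52. The same rule gives 25/49, and the error never exceeds 8% from n = 44 to 52.

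State also that, for this decision, patients without an adequate 18-month assessment count as failures, as in the Protocol summary, so that a binary rule applies. Align section 7.2.1 with this, and keep the Kaplan-Meier rate with its Greenwood interval as the reported estimate, naming its scale. Do not use a log-log interval for the decision, since it still exceeds 8% at n = 45 and 47.

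The cost is wording plus some power at a true rate of 60%: 90.2% instead of 94.3% at n = 50, 90.7% instead of 94.6% at n = 52, 85.6% instead of 91.4% at n = 45, and 86.4% instead of 91.8% at n = 47. Counting missing assessments as failures costs a little more. If, as an illustration, 5% were missing independently of outcome, a true 60% would be observed as 0.60 × 0.95 = 57%.

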Cox regression (Score Test) will be used to compare the experimental versus the control arms adjusted by the stratification factors in randomization (except for centers) at 1-sided 10% significant level.

Toxicity

Analysis for toxicity is based on the safety population. The worst grade of toxicity/adverse events observed over the whole treatment period (excluding re-challenge period for Arm A) according to CTCAE version 4 will be displayed. No formal statistical analysis will be performed to compare toxicity in both arms.

Response Rate

Patients with response categories progression, early death and unknown will be considered as failing to respond to treatment. The response rates in each arm and their 95% confidence intervals will be provided. In addition, response rates in the 2 arms will be compared using a two-sample test at 5% 2-sided level.

Translational research

The translational research is mandatory for this protocol. Any patient who consent to enter the trial will have to consent for the translational research.

Objectives

The main objectives of translational research study are, but not limited to, the following:

 to describe quantitatively the presence of T790M EGFR mutations and original activating EGFR mutations in plasma of patients treated with

- gefitinib and osimertinib longitudinally within the arms and to compare the presence of these mutations across the arms A, B and C.
- to describe the associations between the presence of these mutations and response evaluations by RECIST 1.1 longitudinally within the arms.
- to describe the associations between the presence of these mutations and response and PFS to osimertinib in Arm A, B and C.
- to assess mechanisms of resistance to osimertinib in formalin-fixed paraffin-embedded (FFPE) samples obtained from patients at baseline and at the time of progress on osimertinib by next generation sequencing and compare the presence of molecular resistance alterations in tissue samples and plasma samples taken on progression.

Human Biological material

- plasma sample taken during screening visit and each treatment visit (every 4 weeks) while patients are within active treatment with gefitinib or osimertinib. Note: if gefitinib or osimertinib is temporarily discontinued due to toxicity, plasma sample should still be obtained. The last plasma sample should be taken from patients who progress on osimertinib by RECIST 1.1 evaluation (all three arms).

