8.2 Statistical analysis plan

Analyses described below will be done separately for each arm, except for the secondary endpoint BPFS where comparisons between the arms (i.e. A vs. B, B vs. C and A vs. C) will be conducted.

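### The BPFS test level in 8.2.2 and the summary (1-sided 10%) is not labelled as family-wise, although 8.1.2 designs each of the two formal comparisons at 1-sided 5%

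*Combined protocol and SAP*

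**What the plan says.** **Design (8.1.2).** The tests are announced as: "Formal comparison between arm A versus B and A versus C with respect to BPFS will be made". The error rate is set as: "With a 1-sided alpha = 5% (so that a 1-sided family wise error: 10%, taking into account 2 comparisons". The target is an improvement in 18-month BPFS from 75% to 87.5% (HR 0.46), and "36 BPFS events will give an approximately 70% power to detect the above difference".

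**Analysis (8.2 and 8.2.2).** Section 8.2 makes BPFS the exception to arm-by-arm analysis, "where comparisons between the arms (i.e. A vs. B, B vs. C and A vs. C) will be conducted". Section 8.2.2 adds: "Comparison between arms are foreseen for BPFS endpoint only". Its inference paragraph, whose heading is limited to BPFS, specifies a Cox score test "adjusted by the stratification factors in randomization (except for centers) at 1-sided 10% significant level". It mentions neither the 5% level nor a family-wise rate, and it does not refer back to 8.1.2.

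**Protocol summary (Statistical methods).** The same instruction appears, to "compare the experimental versus the control arms adjusted by the stratification factors in randomization (except for centers) at 1-sided 10% significant level", under a heading that does not mention BPFS. The words experimental and control do not settle the pairs either: the summary's treatment section labels arms A and B as interventions and arm C as the active control.

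**The concern.** The inference paragraph of 8.2.2 is what the analyst will implement. Read by itself, it sets the level of the test, so each comparison would be run at 1-sided 10%. That is twice the per-comparison level in 8.1.2 and would lose the family-wise control that 8.1.2 states.

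At stake is whether a BPFS difference is declared significant. Section 8.1.2 gives this endpoint special emphasis, and under 8.2.2 it is the only time-to-event endpoint compared between arms. A pre-specified test needs a single threshold that is fixed before results are seen.

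**Working it through.** **Inputs.** From 8.1.2: 18-month BPFS of 75% and 87.5%, 36 events, 1-sided 5% per comparison, two comparisons. From 8.1.1: 1:1:1 allocation, hence 1:1 within a pair. From 8.2.2 and the summary: 1-sided 10%.

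**Effect size.** HR = ln(0.875)/ln(0.75) = 0.1335/0.2877 = 0.464, which agrees with the printed 0.46.

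**Reproducing the stated power.** With d = 36 events in the pair compared:

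- Freedman: power = Φ(√d × (1 − HR)/(1 + HR) − z) = Φ(2.196 − z)
- Schoenfeld: power = Φ((√d/2) × |ln HR| − z) = Φ(2.303 − z)

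Here z is 1.645 at 1-sided 5% and 1.282 at 1-sided 10%.

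| Level per test | Freedman | Schoenfeld |
|---|---|---|
| 1-sided 5% | 70.9% | 74.5% |
| 1-sided 10% | 82.0% | 84.6% |

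Using the rounded HR of 0.46 gives 71.7% and 75.3% at 5%. The stated figure of about 70% therefore matches 5% per test.

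**Are the 36 events in one pair?** Section 8.1.2 does not say so. If 36 were the three-arm total, the share in one pair would be about (25 + 12.5)/(25 + 25 + 12.5) = 0.6, or about 22 events. Power at the stated 5% would then be only about 53% to 56%. It would come near 70% (about 67% to 70%) only at 10%, but 8.1.2 attaches its power to 5%. The pairwise reading is the one consistent with that section.

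**Family-wise error, two tests sharing arm A.** The upper bound is the sum of the levels: 5% + 5% = 10%, as stated in 8.1.2, or 10% + 10% = 20%. With equal information per arm (an assumption), the two statistics have correlation 0.5. The error under the global null is 1 − Φ₂(z, z; 0.5), which is 8.8% with 5% each and 16.8% with 10% each.

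**Observed HR needed for significance.** Schoenfeld: exp(−2z/√d). Freedman: (1 − z/√d)/(1 + z/√d).

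| Events in pair | 1-sided 5% | 1-sided 10% |
|---|---|---|
| 36, Schoenfeld | 0.578 | 0.652 |
| 36, Freedman | 0.570 | 0.648 |
| 29, Schoenfeld | 0.54 | 0.62 |

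The row for 29 events shows how the cut-offs move with fewer events. It is roughly what 49 patients per arm and the 18-month minimum follow-up in 8.1.1 would give, assuming exponential BPFS, uniform accrual and no dropout. All cut-offs are unadjusted approximations, whereas the planned test is covariate-adjusted.

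**The case against.** The strongest reply is that nothing is contradictory. Section 8.1.2 gives the per-test level, the family-wise level, the number of tests and the pairs, and the 10% in 8.2.2 equals that family-wise figure. Read together, the sections agree, and only a label is missing. This largely stands. A reader might infer that the plan commits to a 16.8% family-wise error, but the documents do not establish that; it follows only if 10% is applied to each test. What does not stand is that the label is dispensable. The sentence in 8.2.2 gives a level for the test, and following it literally departs from the design.

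Three further inferences are tempting but not supported:

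- **B vs C as a third formal test.** Section 8.1.2 reserves the word formal for A vs B and A vs C, and 8.2 says only that comparisons will be conducted. The natural reading is that B vs C is descriptive. The text should say so, but no redesign of the multiplicity scheme is called for.
- **The interval levels as an error.** The plan states: "Estimates of hazard ratios and their 84% 2-sided CI will be obtained by Cox regression", with 95% intervals in addition. Neither matches a 1-sided 5% test. However, the 84% interval serves as a decision tool only for the primary endpoint, where it matches the 1-sided 8% design. No BPFS decision rests on an interval.
- **An effect on the main result.** BPFS is secondary, and the primary rule for arms B and C does not depend on it.

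**Conclusion.** The point holds as an ambiguity in an operative test instruction, not as a proven contradiction. If 10% is family-wise, nothing in the analysis changes. If it is applied per test as printed, the family-wise error for the two formal pairs roughly doubles, and an observed HR between about 0.58 and 0.65 becomes significant when the design would call it non-significant.

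The power check favours 5% per test as the intended level. The sizes rest on about 36 events in the pair compared, 1:1 allocation, a correlation of 0.5 between the two tests and unadjusted formulas. The consequence is confined to a secondary endpoint, but because a literal reading gives a wrong threshold, the wording should be corrected before BPFS is analysed.

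**What to change.** - **Section 8.2.2 and the protocol summary:** state that BPFS is compared for A vs B and for A vs C by the adjusted Cox score test, each at 1-sided 5% (1-sided family-wise 10%), with longer BPFS in arm A as the alternative. In the summary, limit the paragraph to BPFS.
- **Section 8.2:** mark B vs C as descriptive, reported as HR with confidence interval only.
- **Optional:** add a 90% 2-sided interval for the BPFS hazard ratios, so that the reported interval corresponds to the 1-sided 5% test.

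The cost is wording in three places, with no new data or patients. If 10% was meant as family-wise, the analysis is unchanged. If it was meant per test, each test takes the stricter cut-off (HR about 0.58 rather than 0.65 at 36 events), which is the level for which 8.1.2 states its power.
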